## **11) Outcome Measures:**

### **Outcome 1: Primary Outcome Measure**

Title: HbO during rest before and after stimulation (raw values and change scores)

Description: Prefrontal neural activity will be measured using fNIRS before (baseline) and about 10-15 minutes after the stimulation (delay will be recorded). TBS-induced blood oxygen changes (HbO) at rest will be evaluated in the frontal cortex

Time Frame: baseline, post intervention

### **Outcome 2: Secondary Outcome Measure**

Title: HbO during which participants perform cognitive tasks (e.g., emotional stroop task, verbal fluency task, emotion discrimination task )

Description: Prefrontal neural activity will be measured using fNIRS before (baseline) and about 10-15 minutes after the stimulation (delay will be recorded). TBS-induced blood oxygen changes (HbO) during participants perform the cognitive tasks will be evaluated in the frontal cortex

### **Outcome 3: Secondary Outcome Measure**

Title: Behavioral measures including reaction times and recognition accuracy

Description: Reaction times and accuracy during the cognitive tasks will be evaluated before and after stimulation

## **12) Eligibility:**

Sex (all)

Eligibility Criteria:

Inclusion: : (1) age 18-35, (2) education level of primary six or above, (3) right-handedness, (4) normal or corrected-to-normal vision, (5) being able to understand the verbal instructions, (6) willingness to sign the informed consent form.

Exclusion: (1) a history of seizures, (2) current or past psychiatric disorders, (3) current or past severe internal or neurological illness, (4) ferromagnetic implants <20cm from the head, cardiac pacemaker, deep brain stimulation and other common TMS exclusion criteria, (5) history of substance dependence or abuse within the last 3 months, (6) intake of any medication known to affect the excitation threshold (i.e., benzodiazepines, anticonvulsants).

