**10) Interventions:**

Number of Arms: 4

Allocation: Randomized

Enrollment Type: Anticipated

Number of Subjects: 80 participants with subclinical depression

Arm 1: Control

Arm Title: Priming sham TBS – followed by iTBS after an ISI of 0 minutes

Arm Description: self-explanatory, see Arm Title

Arm 2: Experimental

Arm Title: Priming cTBS – followed by iTBS after an ISI of 0 minutes

Arm Description: self-explanatory, see Arm Title

Arm 3: Experimental

Arm Title: Priming cTBS – followed by iTBS after an ISI of 10 minutes

Arm Description: self-explanatory, see Arm Title

Arm 4: Experimental

Arm Title: Priming cTBS – followed by iTBS after an ISI of 20 minutes

Arm Description: self-explanatory, see Arm Title

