Hypothesis E2 will be supported if there is a significant interaction between time, emotion and conditions 2 and 1.

Hypothesis E3 will be supported if there is a significant interaction between time, emotion and conditions 3 and 1.

Hypothesis E4 will be supported if there is a significant change in condition 4 in some (e.g. sad) but not other emotions (e.g. happy) after stimulation (following a post-hoc 2-way interaction between time and emotion).

Finally, two t-tests comparing ERA- recognition accuracies between subclinically depressed and control participants and between pre and post stimulation in the sample of subclinically depressed participants will be performed in order to test hypotheses E5 and E6, respectively.

Hypothesis E5 will be supported if recognition accuracy is reduced in participants with subclinical depression compared to the control sample.

Hypothesis E6 will be supported if recognition accuracy will be increased after stimulation compared to baseline in participants with subclinical depression.

Behavioral data will be analyzed using the IBM SPSS software (<http://www-01.ibm.com/software/analytics/spss/>). The alpha level will be set at 0.05, adjusted for multiple comparisons using the Bonferroni-Holm procedure. For GLM, post-hoc pairwise comparisons will be corrected using Fisher least significant difference procedure in accordance with the closed test principle, i.e., post hoc comparisons will be declared nonsignificant if the global p value of the main- or interaction effect is nonsignificant, but carried out without further correction in case of a significant global effect.

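### Does the eligibility list need a symptom threshold, and E5 a described control sample, before the plan can be used?

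*Combined protocol and SAP*

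**What the plan says.** Section 4 names subclinical depression as the condition, and section 2 places the research in people who have it. Section 10 fixes enrolment in these terms: "Number of Subjects: 80 participants with subclinical depression".

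Section 12 gives six inclusion criteria. The first four are "1) age 18-35, (2) education level of primary six or above, (3) right-handedness, (4) normal or corrected-to-normal vision"; the other two concern understanding of instructions and consent. Of the six exclusion criteria, one bears on mood: "current or past psychiatric disorders".

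Section 11 lists three outcomes: "HbO during rest before and after stimulation (raw values and change scores"), "HbO during which participants perform cognitive tasks" and "Behavioral measures including reaction times and recognition accuracy".

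Section 13 states two hypotheses by reference to subclinical depression. E5 is supported if "recognition accuracy is reduced in participants with subclinical depression compared to the control sample". E6 is supported if "recognition accuracy will be increased after stimulation compared to baseline in participants with subclinical depression". Section 3 gives no detailed description of its own and points to the ECS proposal.

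**The concern.** Read alone, section 12 describes healthy, right-handed young adults. It caps severity by excluding diagnosed disorder but sets no floor: no scale, minimum score or time of assessment. None of the three outcomes is a symptom score, so the listed outcome data would not show afterwards who had been recruited. If people without symptoms entered, the second objective (reducing negative bias) and E6 would be tested in a group other than the one named.

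E5 looks weaker still. Its comparator has no stated source, size, eligibility or assessment time. Arm 1 carries the label Control but is the sham-priming arm within the 80, so it cannot be the group without subclinical depression. The plan does not say whether controls come on top of the 80.

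**Working it through.** **Count of criteria (section 12).** Inclusion 6 + exclusion 6 = 12. Criteria setting a lower symptom bound: 0. Criteria setting an upper bound, by diagnosis: 1. The literal reading of section 12 is therefore correct.

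**Section 12 beside the rest.** Sections 2, 4 and 10 each name the population, and section 10 attaches it to all 80 participants. An asymptomatic volunteer passes section 12 but contradicts section 10. The sections combine without conflict: section 10 says who is enrolled, and section 12 adds the general and safety conditions. The missing piece is how subclinical depression is ascertained, and section 3 sends the detail to a document not available here.

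**Effect on the primary comparisons.** Suppose a share *f* of those enrolled had no symptoms. Let δ_s and δ_0 be the difference in mean HbO change between two arms among people with and without symptoms. Under randomisation *f* is the same in every arm in expectation, so the expected contrast is

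(1 − *f*)·δ_s + *f*·δ_0.

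This is an unbiased comparison of the arms for the people enrolled, at any *f*. The threshold decides whom the result describes; it does not decide whether the between-arm comparison is fair.

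**Outcomes.** The stated purpose is to optimise stimulation parameters, and the fNIRS measurement comes about 10–15 minutes after stimulation. A symptom outcome is not needed for that purpose. Whether participants had symptoms at entry is a screening matter, so the absence of a symptom outcome repeats the first point and adds nothing to it.

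**E5.** There is no stated figure to reproduce: the plan gives no effect size, power, sidedness or control number for E5. For illustration, take 80 cases and *m* controls, with a two-sided 0.05 level and 80% power. The detectable standardised difference is (1.960 + 0.842)·√(1/80 + 1/*m*):

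- *m* = 20: 2.802 × √0.0625 = 0.70
- *m* = 40: 2.802 × √0.0375 = 0.54
- *m* = 80: 2.802 × √0.0250 = 0.44

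The smallest number of controls for 80% power by t-test, with 80 cases, is:

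| Assumed level | d = 0.5 | d = 0.8 |
|---|---|---|
| one-sided 0.05 | 37 | 12 |
| two-sided 0.05 | 53 | 15 |
| two-sided 0.05/2 = 0.025 | 75 | 19 |
| two-sided 0.05/6 ≈ 0.0083 | 129 | 26 |

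Effect size, sidedness, power and the Holm family are all assumptions; only the 80 comes from the plan. The spread from 12 to 129 shows that the control number is not stated, and nothing more.

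**Count of exploratory hypotheses.** Section 13 introduces three exploratory hypotheses for the mixed models, and then four (E1 to E4) follow. E5 and E6 come afterwards with their own t-tests. Three against four is a clerical slip, and it does not bear on the population or on E5's comparator.

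**The case for a change.** The strongest case for acting is that an eligibility list should let a screener decide. Section 12 looks complete, so a reader would take it as the whole rule. A label in section 10 states intent; it does not say which score qualifies. Without a threshold, nothing listed separates a case from a control in E5, and the results of the second objective and E6 have no stated boundary. Adding one sentence would cost almost nothing.

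The description of the gap stands: these documents give no scale or cut-off. The stronger claim, that the plan would fail to deliver its population, does not. It holds only if section 12 is read without section 10. The suggested sentence would itself leave the cut-off to the sponsor, so it would record a decision already implied and alter neither recruitment nor analysis. A description of the E5 controls is likewise a matter of writing down what is intended: section 13 commits to testing against control participants, so such a sample is evidently planned. Dropping E5 would discard a prespecified exploratory question because a short document does not describe its comparator.

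**Conclusion.** No change to the plan is called for. The gap is real but is one of detail: 0 of 12 criteria set a symptom floor, while the condition, the summary and the enrolment line all restrict the study to subclinical depression. A team following the whole document would screen for it. The randomised resting-HbO comparisons between arms are not biased by the omission at any share of asymptomatic participants. How far the second objective and E6 apply to subclinical depression depends on the definition used at screening, which can be reported with the results.

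E5's undescribed control sample affects one exploratory, non-randomised comparison. Its power cannot be computed from the documents, and the range of 12 to 129 controls rests on assumed inputs.

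This conclusion assumes that the enrolment line in section 10 is applied as a restriction on who may enter. Whether the proposal cited in section 3 holds the scale, the cut-off or the control-group description cannot be checked here.

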## **13) Statistical Analysis Plan:**

fNIRS data analysis will follow the standard processing steps. This includes spatial registration (recording of standard cranial landmarks nasion, inion, left and right ear, and the 3D locations of the fNIRS probes); transformation to MNI space [39]; band-pass

filtering for motion artifact removal; and estimation of the hemodynamic response function using GLM, as implemented in the NIRS Toolbox for MATLAB. Comparisons between baseline and task HbO will reveal task-related de/activations, corrected for multiple comparisons (52 channels). Average HbO changes will then be determined for each channel and each measurement and entered into second-level analysis. Similarly, means of HbO for pre and post-stimulation will be entered into second-level analysis.

A t-test between pre- and post-stimulation in condition 1 will be performed to test hypothesis 1. Hypothesis 1 will be supported if there is a significant increase in prefrontal HbO after stimulation.

A t-test between condition 2 and 1 using change scores will be performed to test hypothesis 2. Hypothesis 2 will be supported if there is a significant stronger change in HbO in condition 1 compared to condition 2

A t-test between condition 3 and 1 using change scores will be performed to test hypothesis 3. Hypothesis 3 will be supported if there is a significant stronger change in HbO in condition 3 compared to condition 1.

A t-test between pre- and post-stimulation in condition 4 and between change scores of condition 1 and 4 will be performed to test hypothesis 4. Hypothesis 4 will be supported if there is a significant increase in prefrontal HbO after stimulation, but no significant difference in change scores between condition 1 and 4.

Regarding the three exploratory hypotheses about participants' behavior (reaction times, hits and misses) and HbO changes during cognitive tasks, linear mixed models will be conducted to determine differences between conditions, followed by post-hoc pairwise comparisons. Here, a three-way interaction between time, condition and emotion will be evaluated and followed by post-hoc two-way interactions and pairwise comparisons.

Hypothesis E1 will be supported if there is a significant change in HbO and/or behavioral measures in condition 1 in some (e.g. sad) but not other emotions (e.g. happy) after stimulation (following a post-hoc 2-way interaction between time and emotion).

Hypothesis E2 will be supported if there is a significant interaction between time, emotion and conditions 2 and 1.

Hypothesis E3 will be supported if there is a significant interaction between time, emotion and conditions 3 and 1.

Hypothesis E4 will be supported if there is a significant change in condition 4 in some (e.g. sad) but not other emotions (e.g. happy) after stimulation (following a post-hoc 2-way interaction between time and emotion).

Finally, two t-tests comparing ERA- recognition accuracies between subclinically depressed and control participants and between pre and post stimulation in the sample of subclinically depressed participants will be performed in order to test hypotheses E5 and E6, respectively.

Hypothesis E5 will be supported if recognition accuracy is reduced in participants with subclinical depression compared to the control sample.

Hypothesis E6 will be supported if recognition accuracy will be increased after stimulation compared to baseline in participants with subclinical depression.

Behavioral data will be analyzed using the IBM SPSS software (<http://www-01.ibm.com/software/analytics/spss/>). The alpha level will be set at 0.05, adjusted for multiple comparisons using the Bonferroni-Holm procedure. For GLM, post-hoc pairwise comparisons will be corrected using Fisher least significant difference procedure in accordance with the closed test principle, i.e., post hoc comparisons will be declared nonsignificant if the global p value of the main- or interaction effect is nonsignificant, but carried out without further correction in case of a significant global effect.

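### The only motion-artifact step named for fNIRS is a band-pass filter, which cannot remove movement in the task band; an explicit correction would be a cheap gain for task HbO (low severity)

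*Combined protocol and SAP*

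**What the plan says.** Section 13 opens by saying "fNIRS data analysis will follow the standard processing steps" and then lists what these include: spatial registration, transformation to MNI space, band-pass "filtering for motion artifact removal; and estimation of the hemodynamic response function using GLM", the last "as implemented in the NIRS Toolbox for MATLAB". The motion role is given to the filter, and the next step is the GLM. There are no filter cut-offs, no detection or correction of shifts or spikes, and no mention of robust or prewhitened regression.

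The task contrast is then interpreted directly: "Comparisons between baseline and task HbO will reveal task-related de/activations, corrected for multiple comparisons (52 channels").

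Under section 11, Outcome 2 (secondary) is "HbO during which participants perform cognitive tasks (e.g., emotional stroop task, verbal fluency task, emotion discrimination task"). The primary outcome is separate: "HbO during rest before and after stimulation (raw values and change scores"). Differences in task HbO between conditions go to linear mixed models in which "a three-way interaction between time, condition and emotion will be evaluated". Section 13 calls these hypotheses exploratory.

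Section 3, Detailed Description, refers the reader to a proposal that is not among the supplied documents.

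**The concern.** A band-pass filter separates signals by frequency, not by source. If the band is wide enough to keep a block-task haemodynamic response, it also keeps whatever part of a sensor shift or slow movement lies at the same frequencies, and it spreads an abrupt shift over neighbouring seconds. It removes only what lies outside the band, such as slow drift and cardiac pulsation. The filter therefore cannot do the job the plan assigns to it. This is a weakness of the stated method, not just a missing detail.

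What is at stake is the task HbO estimate. Movement that follows the task timing in a consistent direction would enter the GLM coefficient and be read as activation. Movement without that pattern would add error variance.

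**Working it through.** The plan states no figure on this point, so there is none to reproduce. The check is a simulation of the mechanism.

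**From the documents.** Band-pass filtering is the only motion step named, a GLM follows, and the task contrast is computed per channel (section 13). The tasks are those listed under Outcome 2.

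**Assumed, because the documents do not give them.** Zero-phase third-order Butterworth filter; 10 Hz sampling; pass-bands 0.005-0.1, 0.01-0.1, 0.01-0.2 and 0.01-0.5 Hz; task/rest blocks of 30/30 s or 60/60 s; double-gamma response function; ordinary least squares. Artifact size is in arbitrary units.

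**Step 1: what the filter leaves (0.01 Hz low cut).**

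| Artifact | High cut 0.1 Hz | 0.2 Hz | 0.5 Hz |
|---|---|---|---|
| Unit step, residual peak | 0.47 | 0.51 | 0.54 |
| Unit 5-s deflection, height kept | 77% | 102% | 96% |
| 0.5-s spike, peak kept | 9% | 20% | 49% |

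The step residual stays above 0.1 for about 44 s. Brief spikes are much reduced in height at the lower high cuts; shifts and several-second movements are not.

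**Step 2: what the GLM makes of it.** Let x be the task boxcar convolved with the response function, a the artifact, and F the filter, applied to both. True activation is zero, so the coefficient

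β = cov(F[x], F[a]) / var(F[x])

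should be 0. With a equal to 1 during every task block and 0 otherwise:

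| Pass-band (Hz) | β, 30-s blocks | β, 60-s blocks |
|---|---|---|
| 0.005-0.1 | 0.717 | 0.846 |
| 0.01-0.1 | 0.708 | 0.492 |
| 0.01-0.2 | 0.690 | 0.474 |
| 0.01-0.5 | 0.687 | 0.481 |
| Unfiltered | about 0.74 | about 0.87 |

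The unfiltered values move by a few hundredths with the layout of the run. The share surviving is 0.69/0.74 = 93% to 0.72/0.74 = 97% with 30-s blocks, and 0.47/0.87 = 54% to 0.85/0.87 = 98% with 60-s blocks.

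The spread at 60 s comes from the low cut. The 60/60 design repeats at 1/120 = 0.0083 Hz, which lies below a 0.01 Hz cut but above 0.005 Hz. The 30/30 design repeats at 1/60 = 0.0167 Hz, inside every band tried.

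**Step 3: movement without that pattern.**
- A unit step at a random time: mean β 0.00-0.01, SD 0.04-0.06.
- Spikes of height 5 with random sign, or not timed to the task: mean β within about 0.02 of zero, SD 0.05-0.13.
- A unit 2-s movement at each block onset: β from -0.03 to -0.12, which is small and in the opposite direction.
- Six same-sign spikes of height 5 spread through each task block: mean β 0.35-0.36 (30 s) and 0.12-0.21 (60 s).

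False activation therefore needs movement in one direction, held or repeated through the task blocks.

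**Step 4: carrying it to the hypotheses.** Write m for the movement contribution to β. Its contribution to a within-arm time × emotion term (E1, E4) is

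(m post, sad − m pre, sad) − (m post, happy − m pre, happy).

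This is zero if movement is the same at both times, or the same for both emotions. E2 and E3 take a further difference between arms, so movement common to the arms also cancels. The baseline-versus-task activation contrast has no such protection.

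**The case against.** **Unstated steps.** The processing list is introduced as what the standard steps include, it points to a toolbox, and the detailed description sits in a proposal not supplied. A reader might infer that the trial will do nothing else about motion. The documents do not support that; they show only that the plan commits to nothing else. Naming a toolbox does not fix which of its options will be used.

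**Size.** A reader might infer that any speech or head movement will be read as activation. Step 3 shows otherwise. The large coefficients in step 2 are close to built in, because the artifact has the same block shape as the regressor. Block lengths, cut-offs and artifact shape are assumed, and nothing relates the artifact's size to a real HbO effect. The figures show how much of such an artifact the filter leaves, not how large the bias in this trial would be.

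**Speech.** Verbal fluency is the obvious candidate for task-locked movement, but it appears only as an example, the documents do not say that responses are spoken, and no emotion factor is described for it. The E1-E4 rules concern emotion-specific change.

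**Bias between arms.** A reader might infer that comparisons of conditions are biased. Allocation is randomised, every arm receives iTBS, and the documents give no reason for movement to differ by arm. Movement common to times, emotions or arms cancels as in step 4.

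All four objections limit the consequence. None of them makes a band-pass filter able to remove in-band movement.

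**Conclusion.** The concern stands as a low-severity, cheap improvement to the analysis of task HbO, a secondary outcome whose hypotheses are exploratory. The filter cannot remove in-band movement. Under the assumed settings, between about half and nearly all of a sustained task-locked offset reaches the GLM coefficient. Whether that matters here depends on whether such movement occurs and, for E1-E4, on whether it differs by time, emotion or arm; the documents settle neither. Otherwise the main cost is noise.

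A reader might extend the point to the primary outcome, since the same filter is the only motion step named there too. The mechanism shown depends on task timing, which resting recordings do not have, so it does not show that the resting result is biased.

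**What to change.** In section 13:

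1. Describe the band-pass filter as removing slow drift and cardiac noise, and state its cut-offs.
2. Before filtering, apply a pre-specified correction of detected shifts and spikes (for example derivative-based, spline or wavelet) to the optical-density signal. Fix the detection rule in advance and apply it blind to condition.
3. Estimate the task GLM with prewhitened, iteratively reweighted (robust) regression.

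If the proposal cited in section 3 already contains a motion step, carrying it into section 13 may need only a sentence.

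The cost is SAP wording and one or two more processing steps on recordings that will be made anyway. Recruitment, visits and stimulation are unaffected. The downside is that some true signal will be down-weighted. These steps also cannot fully separate a movement that closely mimics the slow response, so they reduce the problem without removing it. Settling them before the data are analysed by condition also closes off a later choice of motion pipeline.

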**4) Primary Disease or Condition being studied in the trial, or the focus of the study:**  
Subclinical Depression

**5) Keywords:** Priming Stimulation, Theta-Burst Stimulation, Functional NIRS, Emotion Discrimination, Subclinical depression

**6) Primary Purpose:** Optimization of stimulation parameters for a priming stimulation protocol

**7) Study Phase:** N/A

**8) Intervention Study Model:** Parallel, sham-control

**9) Model Description:** (Objectives)

The proposed research has two primary objectives.

The first objective is to understand the effects of priming stimulation timing of the left DLPFC using fNIRS at rest. The time window between priming cTBS and test iTBS will be either 0, 10, or 20 minutes. We hypothesize that 0 minutes will eliminate the effect of the test iTBS, whereas 10 minutes will potentiate it; 20 minutes will have no effect (i.e., result in no difference, relative to sham priming).

The second objective is to evaluate the effects of priming stimulation in the context of facial emotion processing and executive function in subclinical depression. Previous evidence indicates that DLPFC stimulation modulates affective processing on the neural and behavioral level. We hypothesize that optimal priming stimulation will affect reaction times in an emotion-specific way and will reduce the negative bias observed in subclinical depression.

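### The rule for hypothesis 2 can show that 0-minute priming weakens the iTBS response, not that it eliminates it

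*Combined protocol and SAP*

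**What the plan says.** Section 9 (Model Description) gives the prediction under the first objective: "We hypothesize that 0 minutes will eliminate the effect of the test iTBS, whereas 10 minutes will potentiate it".

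Section 10 (Interventions) defines the two arms concerned. Arm 1, the control, is "Arm Title: Priming sham TBS – followed by iTBS after an ISI of 0 minutes". Arm 2 is "Arm Title: Priming cTBS – followed by iTBS after an ISI of 0 minutes".

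Section 13 (Statistical Analysis Plan) gives the test, "A t-test between condition 2 and 1 using change scores will be performed to test hypothesis 2", and then the decision rule, "Hypothesis 2 will be supported if there is a significant stronger change in HbO in condition 1 compared to condition 2". Nothing further is required for hypothesis 2.

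The rule for hypothesis 4 is built differently: "A t-test between pre- and post-stimulation in condition 4 and between change scores of condition 1 and 4 will be performed to test hypothesis 4". A pre-post test, in condition 1, also underlies hypothesis 1.

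**The concern.** Elimination is a statement about one arm: after 0-minute cTBS priming, no response to iTBS is left. A significant difference between conditions 1 and 2 is a statement about two arms: one responds more than the other. The second does not imply the first. Condition 2 could keep half of the sham-primed response, and show a clear rise of its own, and the rule would still be met.

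The contrast with hypothesis 3 helps. Potentiation is relative, so a comparison with condition 1 suits it. Elimination is absolute, and the same kind of comparison does not suit it.

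The matter bears on the first of the two primary objectives and on the primary outcome, resting HbO. The Brief Summary expects the findings to identify the best interval and to validate homeostatic metaplasticity in the left DLPFC. Whether immediate priming abolishes the response or only weakens it is part of that conclusion.

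**Working it through.** **No planned figure to reproduce.** The document gives no effect size, SD, margin, power or sample-size derivation. The mismatch is one of logic and needs no number; what follows only shows how much it could matter.

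**1. Prediction against rule**

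| | Prediction (section 9) | Rule (section 13) |
|---|---|---|
| Quantity | change left in condition 2 | condition 1 change minus condition 2 change |
| Claim | it is zero | it is significantly above zero |
| Limit on the change left in condition 2 | implied | none |

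**2. Inputs**
- Section 10: "Number of Subjects: 80 participants with subclinical depression" and "Number of Arms: 4". Assuming equal allocation (no ratio is stated), 80 / 4 = 20 per arm.
- Alpha 0.05 with Bonferroni-Holm (section 13). Two-sided testing is assumed. If four tests form the family, the strictest Holm step is 0.05 / 4 = 0.0125.
- Also assumed: equal SD of change scores in both arms, one HbO summary measure, no dropout, and the rule read as a larger rise in condition 1.
- Condition 1 effects of 0.5 to 1.8 SD are assumed values, with the true effect halved in condition 2.

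**3. What the rule demands.** The smallest significant difference is t(0.975; 38 df) × √(2/20) = 2.024 × 0.316 = 0.64 SD. The change in condition 2 enters only through this difference.

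**4. Probability of support when the effect is only halved.** With condition 1 effect d, the true difference is d/2. The test statistic follows a noncentral t with 38 df and noncentrality (d/2) × √(20/2). For d = 1.0 this is 0.5 × 3.162 = 1.58, and the chance of exceeding 2.024 is 0.338. For d = 1.8 it is 0.9 × 3.162 = 2.85, and the chance is 0.792.

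| Condition 1 effect (SD) | Left in condition 2 (SD) | Supported, alpha 0.05 | Supported, alpha 0.0125 |
|---|---|---|---|
| 0.5 | 0.25 | 12% | 4% |
| 0.8 | 0.40 | 23% | 10% |
| 1.0 | 0.50 | 34% | 16% |
| 1.5 | 0.75 | 64% | 41% |
| 1.8 | 0.90 | 79% | 59% |

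**5. Support while condition 2 itself rises significantly.** By simulation (200,000 runs, two-sided 0.05 for both tests), hypothesis 2 is supported and condition 2 also shows a significant pre-post rise in about 10% of trials at 1.0 SD, 53% at 1.5 SD and 76% at 1.8 SD. At 0.8 SD it is about 2.5%, and at 0.5 SD about 0.1%.

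**6. What showing elimination would take.** With 20 in condition 2, the 90% CI half-width for its mean change is 1.729 × 1/√20 = 0.39 SD. If the true residual is exactly zero, two one-sided tests (TOST) succeed in about 12% of trials at a margin of 0.4 SD, 39% at 0.5 SD, 65% at 0.6 SD and 89% at 0.75 SD.

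**The case against.** **Hypothesis 2 is not written out.** Section 3 refers the detailed description to a separate proposal. If that proposal words hypothesis 2 as a weaker response than after sham priming, the rule fits it and only the wording in section 9 is loose. This stands as a caveat. The inference is still a clear one: hypothesis 2 compares conditions 2 and 1, and section 9 makes only one prediction for 0 minutes.

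**The SAP does not say that elimination will be declared.** A reader might infer that it commits the team to reporting elimination. It does not; it says that the hypothesis will be supported. What can be said is that support for the section 9 prediction, taken at its word, is support for elimination.

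**Condition 1 might show no rise while condition 2 falls.** A reader might infer that the rule then finds elimination where there was nothing to eliminate. The text does not settle this. By magnitude, the stronger change is then in condition 2 and the rule fails; only on a signed reading is it met. Hypothesis 1 would also expose the case: with true changes of 0 and −0.9 SD, hypotheses 1 and 2 are both supported in only about 2.5% of trials. No formal gate links the two, which is a reason to read them together, but this scenario is not a basis for the point.

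**The residual would be visible anyway.** Outcome 1 covers raw values and change scores, so condition 2's change is already a planned measure. That is true and limits the harm. A confidence interval for that change and a criterion for interpreting it are what the plan lacks.

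**The high percentages need large effects.** This also stands. The 79% requires a 1.8 SD effect and no Holm adjustment, so the whole range should be read.

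**Conclusion.** The point holds as a mismatch between a prediction and its decision rule. The section 13 test can establish that 0-minute cTBS priming attenuates the HbO response relative to sham priming. It cannot establish elimination, because it places no limit on what remains in condition 2.

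The practical size depends on an effect that the document does not give. It is modest if the condition 1 response is below about 1 SD or alpha is at its strictest Holm step, and considerable if the response is 1.5 SD or more. All of this rests on equal allocation, equal SDs and a halved true effect. The logical point rests on none of these, only on the inferred link between hypothesis 2 and the section 9 sentence.

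The test, the data and the estimate are sound as planned. What should change is the conclusion drawn from them.

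**What to change.** 1. Keep the t-test between conditions 1 and 2. State the direction of the difference in terms of a rise in HbO.
2. Word the conclusion as: 0-minute cTBS priming reduces the HbO response to iTBS relative to sham priming.
3. Interpret it alongside the hypothesis 1 result, since a reduction means little if condition 1 shows no response.
4. Report condition 2's mean pre-post change with its 95% CI.
5. Do not conclude elimination from this test. If the word is kept, require that hypothesis 1 is supported and that condition 2's change lies within a prespecified two-sided equivalence margin around zero. A one-sided upper limit would not do, because a fall below baseline would pass it. A non-significant pre-post test in condition 2 would not do either.
6. Write hypotheses 1 to 4 out in the SAP, so that each rule can be read against its claim.

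The cost is a few lines of SAP text and one confidence interval from data already being collected. The downside is that, at about 20 per arm, elimination could be shown only with a wide margin, so the weaker wording will usually be the one that the data can carry.
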